### 14.1.3. DERIVATIONS

Based on the aforementioned, the following variables, as presented in the planned TLF shells, will be derived for post-vaccination visits and/or time points:

- QFT-GIT testing compliance derived per visit:
  - o Yes: QFT-GIT assessment date is within the protocol-defined visit window.
  - o No: QFT-GIT assessment date is outside the protocol-defined visit window.
  - o Missing: The participant is expected to have a QFT-GIT assessment available.
  - o Refer to APPENDIX 8: Protocol-defined Visit Windows for the relevant protocol-defined visit windows.
- QFT-GIT result classification at each visit (use the retest result if available). The Investigator's assessment will be used, which is based on the algorithm below.

QFT-GIT Result Classification	QFT Nil	QFT Ag - QFT Nil	QFT Mitogen - QFT Nil
Positive	≤ 8.0	≥ 0.35 (primary analysis threshold) and ≥ 25% of QFT Nil value	Any
Negative		< 0.35 (primary	≥0.5

Document: Aeras\_C-040-404\_SAP\_V2\_0

Author: [name]

Version Number:

2.0

Version Date:

29SEP2017

Template No: CS\_TP\_BS016 – Revision 3

Reference: CS\_WI\_BS005

Effective Date: 01May2012

Copyright © 2012 Quintiles Transnational Corp. All rights reserved.

The contents of this document are confidential and proprietary to Quintiles Transnational Corp. Unauthorized use, disclosure or reproduction is strictly prohibited.

QFT-GIT Result Classification	QFT Nil	QFT Ag - QFT Nil	QFT Mitogen - QFT Nil
Indeterminate		analysis threshold) OR ≥ 0.35 (primary analysis threshold) and < 25% of QFT Nil value	< 0.5
Indeterminate	> 8.0	Any	Any

- If the QFT-GIT result is indeterminate at any of the visits Day 84, M6, M9, M12, M15, M18, M21, M24, M27 or M30, the QFT-GIT test will be repeated (QUANT2 form in the eCRF used to record the result). If the repeat result is negative or indeterminate, the participant will continue with the study visits as if the participant did not convert, and the result for the corresponding visit will be deemed “negative”.
- Any QFT-GIT conversion status:
  - o The QFT-GIT conversion status is assigned hierarchically in the order provided below:
    - Yes: Participant has at least one positive QFT-GIT result classification, regardless of missing or indeterminate results at any other visit and regardless of at which visit the positive QFT-GIT result is recorded.
      - Post-Day 84 QFT-GIT conversion: First positive QFT-GIT result classification recorded post-Day 84.
      - Early QFT-GIT conversion: First positive QFT-GIT result classification recorded at Day 84.
    - No: Participant has no positive QFT-GIT result classification and the last available QFT-GIT result classification is negative.
    - Missing: Participant has no positive/negative/indeterminate QFT-GIT result classification available.
- Censored:
  - o Participants who do not experience a primary endpoint or early conversion (early conversion is only applicable to the analyses based on the Randomized analysis set), will be censored at the date of their last available, non-positive QFT-GIT result.
  - o The following SAS code will be implemented for all Kaplan-Meier analyses, where:
 

```
PROC LIFETEST DATA = <>;
    TIME Months*Censored(1);
    TEST Treatment_Group;
RUN;
```

    - Censored = 1 represents censored participant.
    - Censored = 0 represents participant who experienced an event.
    - Months represent the available follow-up time (months) per participant since:
      - Day 84 (applicable to analyses based on the mITT and PP analysis set).
      - Randomization (applicable to analyses based on the Randomized analysis set).
- Event:
  - o Participants who experience a primary endpoint or early conversion will be indicated as having an event (depending on the relevant table, early converters will be included/excluded from the participants experiencing an event).

Document: Aeras\_C-040-404\_SAP\_V2\_0

Author: [name]

Version Number:

2.0

Version Date:

29SEP2017

Template No: CS\_TP\_BS016 – Revision 3

Reference: CS\_WI\_BS005

Effective Date: 01May2012

Copyright © 2012 Quintiles Transnational Corp. All rights reserved.

The contents of this document are confidential and proprietary to Quintiles Transnational Corp. Unauthorized use, disclosure or reproduction is strictly prohibited.

- Available follow-up time (months) until first QFT-GIT conversion:
  - o The number of months of follow-up time will be derived for each participant based on the date of randomization/Day 84 (depending on the relevant table) and either the censor or event date.
  - o 1 month = 4 weeks.
  - o For the sensitivity analysis the follow-up time will be rounded to the nearest 6-month interval for any of the following visits:
    - Month 6.
    - Month 12
    - Month 18.
    - Month 24.
  - o For the sensitivity analysis the following SAS code will be implemented:

```
PROC LIFETEST DATA = <> METHOD=lt INTERVALS=(0 to 2 by 0.5)
PLOTS=(s) ;
TIME Years*Censored(1) ;
FREQ count;
RUN;
```

- Vaccine efficacy is derived as:
  - o  $VE = 1 - \text{Hazard Rate Ratio (Vaccine/comparator)}$
  - o The hazard ratio is estimated based on the following Cox regression model:

```
PROC PHREG DATA = <>;
MODEL Time to Event (Months) * Censor (1) = Treatment Group;
RUN;
```

- Censor = 1 represents censored participant.
    - Censor = 0 represents participant who experienced an event.
    - Months represent the available follow-up time (months) per participant since randomization.
  - o The 80% CI is based on the two-sided hazard ratio confidence interval and will be derived as:
    - $VE_{\text{lower limit}} = 1 - \text{Hazard ratio}_{\text{upper limit}}$
    - $VE_{\text{upper limit}} = 1 - \text{Hazard ratio}_{\text{lower limit}}$
  - o The 95% CI is based on the two-sided hazard ratio confidence interval.

- For the sensitivity analysis, interval censoring will be used based on the following code:

```
PROC ICPHREG DATA = <>;
MODEL (left, right) = Treatment Group /b=pch(NINTERVAL=X);
RUN;
```

- Left represents left censoring value in months.
  - Right represents right censoring value in months.
  - Left and right censoring values are dependent on where the event is identified:

Visit at Which Primary Event Identified	Left Censoring Value	Right Censoring Value
M6	3	6
M12	6	12
M18	12	18
M24	18	24

Document: Aeras\_C-040-404\_SAP\_V2\_0

Author: [name]

Version Number:

2.0

Version Date:

29SEP2017

Template No: CS\_TP\_BS016 – Revision 3

Reference: CS\_WI\_BS005

Effective Date: 01May2012

Copyright © 2012 Quintiles Transnational Corp. All rights reserved.

The contents of this document are confidential and proprietary to Quintiles Transnational Corp. Unauthorized use, disclosure or reproduction is strictly prohibited.

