### 7.3 Prevention of Infection (QFT-GIT Conversion) Analyses

The primary *Mtb* infection endpoint will be QFT-GIT conversion from a negative to positive test, using the manufacturer's recommended threshold of 0.35 IU/mL, at any time-point after Day 84 and through end of follow-up for the primary endpoint (see below). The frequency of QFT-GIT negativity/positivity will be summarized for each treatment group at screening, on Day 84, on Month 6, and for all subsequent assessments. The log-rank statistic will be used to test the null hypothesis of no difference in the rates of *Mtb* infection over the follow-up period between each of the AERAS-404 and BCG groups compared to the placebo group. The log-rank test statistic compares estimates of the hazard functions of the vaccine groups at each observed event time. It is constructed by computing the observed and expected number of events in the groups at each observed event time and then summing these to obtain an overall summary across all time points where there is an event. As subjects convert their QFT-GIT tests over time (experience a primary endpoint) or are lost to follow up the number of subjects at risk over time will change. As this is a proof of concept study, these two log-rank tests (AERAS-404 compared to placebo and BCG revaccination compared to placebo) will be performed with a 1-sided Type 1 error of 0.1. There will be no adjustment for multiplicity to control the Type 1 error rate over the two tests. The rationale for not performing this adjustment is related to the fact that the tests pertain to efficacy assessments of two unrelated vaccines. If these two evaluations were performed in two separate trials then no adjustment for multiplicity would be made. Thus, one should not be compelled to adjust for this multiplicity simply because the two evaluations are performed administratively in a single trial.

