## 7.6 Sample Size Considerations

Sample size for the trial is based on the power to detect a reduction in the rate of infection with *Mtb*, as determined by QFT-GIT conversion. As a proof of concept study looking for evidence of biologic impact, the trial is designed to distinguish a QFT-GIT conversion rate reduction of 50% compared to placebo for each vaccine (AERAS-404 and BCG) with power of 80% and a type 1 error rate of 10% (1-sided).

Trial design calculations are performed by computer simulation. The simulations estimate the statistical operating characteristic of a conditional binomial test which, due to relative rarity of the endpoint, provides an excellent approximation to the operating characteristic of the log-rank tests which will be used in the analyses of trial data. The following assumptions, based on preliminary data from SATVI (Mahomed et al, 2011b) were used in these simulations:

- Primary *Mtb* infection endpoint rate = 10% per year
- Rate of loss to follow up = 7% per year
- Average rate of enrollment = 20 subjects per week
- Maximum duration of follow up to primary conversion = 24 months with 6-monthly study visits

Under these assumptions, a total sample size of 990 is expected to provide 64 primary QFT-GIT conversion endpoints approximately 21 months after the first subject is enrolled. Follow up will continue until 64 endpoints are accrued and a median follow up duration of 15 months for individual subjects have both occurred. A 10% rate of QFT-GIT conversions per year is conservative (SATVI data have shown an average 17% conversion rate in adolescents); however, continuing to follow subjects until the required number of endpoints is accrued ensures adequate power for the primary endpoint.

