**Study Day 84 (Subjects receiving AERAS-404 or placebo)**

*Allowable window for clinic visit is 28±5 days from Day 56*

1. Interval medical history and, if indicated by history, focused physical examination.
2. Monitor participant for unsolicited adverse events; record concomitant medications
3. Monitor participant for serious adverse events, adverse events of special interest, and SUSARs; record concomitant medications
4. Monitor participant for solicited injection site reaction adverse events at Study Day 56 injection site; record concomitant medications
5. Complete Study Day 56 injection site examination (with photograph if there is a visible injection-site abnormality; see Section 5.7 for further details)
6. TB symptom screen
7. Blood collection for
  - QuantiFERON®-TB Gold In-Tube
  - Whole blood for evaluation of IGRA

**Study Month 6, 12, 18 and 24 (Study Days 168, 336, 504, and 672) (Subjects receiving AERAS-404 or placebo; to be completed by subjects who did not convert from QFT-GIT(-) to QFT-GIT(+) at the previous visit)**

*Allowable window for clinic visit is 6, 12, 18, or 24 months (168, 336, 504, 672 days) ±14 days from Day 0*

1. Interval medical history and, if indicated by history, focused physical examination.
2. Monitor participant for serious adverse events, adverse events of special interest, and SUSARs; and record concomitant medications
3. TB Symptom Screen
4. Blood collection for
  - QuantiFERON®-TB Gold In-Tube
  - Whole blood for evaluation of IGRA
  - [Study Months 6 and 12 only]PBMC and plasma for correlates of risk protection
  - Whole blood for RNA extraction/absolute blood count

**Study Month 8 (Study Day 224) (Subjects receiving AERAS-404 or placebo; to be completed by subjects who converted from QFT-GIT(-) to QFT-GIT(+) at Study Day 84)**

*Allowable window for clinic visit is 6 months (168 days)  $\pm$ 14 days from Day 56*

1. Monitor participant for serious adverse events, adverse events of special interest, and SUSARs; record concomitant medications
2. TB symptom screen

**84 and 168 Days after conversion from QFT-GIT(-) to QFT-GIT(+) at Months 6-24 (Subjects receiving AERAS-404 or placebo; to be completed by subjects who converted from QFT-GIT(-) to QFT-GIT(+) at Month 6-24 visits)**

*Allowable window for clinic visit is 84 or 168 days  $\pm$ 14 days after conversion*

1. Monitor participant for serious adverse events, adverse events of special interest, and SUSARs; record concomitant medications

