  - o As a sensitivity analysis the content of this table will be repeated in a separate table using interval censoring for the MITT analysis set.
- First QFT-GIT conversion by visit:
  - o Number and percentage (%) of participants with first QFT-GIT conversion at each of the scheduled visits.
  - o Number of participants at risk for first conversion at each scheduled visit.
  - o At risk defined as participants with:
    - A negative QFT-GIT result at the preceding visit without a previous positive QFT-GIT result.
    - A QFT-GIT result available at the relevant visit.
  - o This table will be repeated for the Per Protocol analysis set.
- Follow-up time until first QFT-GIT conversion:
  - o Number of participants contributing to the total follow-up time (at risk).
  - o Cumulative number of participants:
    - Censored (not due to a primary endpoint at the time of the last available non-positive QFT-GIT result).
    - With an event (primary endpoint).
  - o The total follow-up time (person-months), as measured from Randomization (1 month = 4 weeks).
  - o The Kaplan-Meier event rate presented at each relevant post-Day 84 visit.
  - o This table will be repeated for the Per Protocol analysis set.

Document: Aeras\_C-040-404\_SAP\_V2\_0

Author: [name]

Version Number:

2.0

Version Date:

29SEP2017

Template No: CS\_TP\_BS016 – Revision 3

Reference: CS\_WI\_BS005

Effective Date: 01May2012

Copyright © 2012 Quintiles Transnational Corp. All rights reserved.

The contents of this document are confidential and proprietary to Quintiles Transnational Corp. Unauthorized use, disclosure or reproduction is strictly prohibited.

- Primary endpoints by school/region:
  - o Number and percentage (%) of participants who experienced a primary endpoint in each school/region.
- Primary endpoints by site and sex:
  - o Number and percentage (%) of participants who experienced a primary endpoint in each site/sex.

The following table will be presented for the Randomized analysis set:

- QFT-GIT conversion rates including all post-Day 0 conversions:
  - o Number and percentage (%) of participants in each conversion status category:
    - Yes.
    - No.
    - Missing.
  - o Two groups of conversion time points included:
    - Any QFT-GIT conversion (early [Day 84] or post-Day 84) (at risk participants include all participants).
    - Early (Day 84) conversion (at risk participants include all participants).
  - o Hazard ratio (H4:IC31/comparator) presented:

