### 14.2.2. ANALYSIS OF SECONDARY EFFICACY ENDPOINT

The following table will be presented for the Modified Intent-to-treat analysis set:

- QFT-GIT 6-month sustained conversion rates:
  - o Number and percentage (%) of participants in each conversion status category:
    - Yes.
    - No.
    - Missing.
  - o Hazard ratio (H4:IC31/comparator) presented:
    - Point estimates (based on the Cox regression model).
    - P-values for the comparison of the estimated hazard ratios of QFT-GIT 6-month sustained conversion based on a one-sided log-rank test.
      - H4:IC31 versus Placebo.
      - BCG versus Placebo.
      - H4:IC31 versus BCG (at the request of the sponsor's partner).
  - o Vaccine efficacy presented:
    - Point estimate (based on the hazard ratio estimate).
    - 80% two-sided CI based on the hazard ratio estimate from the Cox regression model.
  - o This table will be repeated for the alternative threshold value.
  - o These tables (based on the original threshold as well as the alternative threshold) will be repeated for the Per Protocol analysis set. This table (based on the original threshold) will also be repeated for the Adjusted Modified Intent-to-treat (First Recall Positive Omit) analysis set and the adjudication approach (refer to Section 3.3: Changes to Analysis from Protocol).
  - o As a sensitivity analysis both of these tables (original threshold and the alternative threshold outputs) will be repeated in separate tables using interval censoring for the MITT analysis set.

---

Document: Aeras\_C-040-404\_SAP\_V2\_0

Author: [name]

Version Number:

2.0

Version Date:

29SEP2017

Template No: CS\_TP\_BS016 – Revision 3

Reference: CS\_WI\_BS005

Effective Date: 01May2012

Copyright © 2012 Quintiles Transnational Corp. All rights reserved.

The contents of this document are confidential and proprietary to Quintiles Transnational Corp. Unauthorized use, disclosure or reproduction is strictly prohibited.

The following figures will be presented for the Modified Intent-to-treat analysis set:

- Time to 6-month sustained QuantiFERON conversion:
  - o Kaplan-Meier plots per treatment group for the following:
    - Time to first of three consecutive post-Day 84 QFT-GIT positive results.
  - o Time to sustained QFT-GIT conversion will be presented in months, measured from Day 84 (1 month = 4 weeks) to the date of the first of three consecutively positive QFT-GIT results.

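### Kaplan-Meier curves built on exact test dates overstate cumulative conversion inside the Month 24 window (median about 25-26% against a true 14.9% at planning rates), and the per-visit Kaplan-Meier table has no defined read-off time

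*SAP*

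**What the plan says.** SAP 14.1.3 defines the time variable by calendar dates. "The number of months of follow-up time will be derived for each participant based on the date of randomization/Day 84" and the participant's own event or censoring date. Participants without an event "will be censored at the date of their last available, non-positive QFT-GIT result". PROC LIFETEST with its default product-limit method is specified for all Kaplan-Meier analyses. The clock starts at Day 84 for the mITT and per-protocol sets.

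The tests come on a fixed schedule with a tolerance. Protocol Appendix A states "Allowable window for clinic visit is 6, 12, 18, or 24 months (168, 336, 504, 672 days", each ± 14 days from Day 0, and SAP Appendix 8 repeats these windows. Footnote d to Protocol Tables 3-1 and 3-2 makes Month 24 the final visit for those who remain negative.

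The outputs are per-arm Kaplan-Meier figures and, in the follow-up-time table of SAP 14.1.2, "The Kaplan-Meier event rate presented at each relevant post-Day 84 visit". That table counts months from randomization, at 4 weeks per month, whereas SAP 14.1.3 gives the Day 84 clock for mITT analyses. Neither section says at which time the rate for a visit is read. For the secondary endpoint the figure shows "Time to first of three consecutive post-Day 84 QFT-GIT positive results", with similar date-based censoring in SAP 14.2.3. Rounding to visits and interval censoring appear only as sensitivity analyses.

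**The concern.** Conversion is seen only when a test is done, and the tests for one visit are spread over 29 days. At Months 6, 12 and 18 this is harmless once the window has closed: someone who tests negative early in the window stays at risk, so the completed step has the right denominator. At Month 24 it is not harmless. Someone negative on day 660 leaves the risk set that day and is missing from the denominator when another participant converts on day 680. The Month 24 conversion probability is thus applied again and again to a shrinking group.

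The SAP covers the final analysis, after follow-up is complete, so nearly every never-converter still in the study leaves in this one window. The end of each curve is then inflated and depends heavily on who happened to attend last. A reader of the figure would take from it a cumulative infection rate well above the true one.

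**Working it through.** **Inputs.** Protocol 7.6: conversion 10% per year, loss 7% per year. Protocol 2.2: 330 per arm. SAP Appendix 8: Month 24 at day 672 ± 14, Day 84 ± 7. The documents do not give the spread of test dates within a window. It is assumed here to be either uniform or clustered around the target day.

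**The plan's own figure.** The documents state no cumulative Kaplan-Meier rate, so the only figure to reproduce is the 64 endpoints. The tests "will be performed with a 1-sided Type 1 error of 0.1", and the design aims to "distinguish a QFT-GIT conversion rate reduction of 50% compared to placebo for each vaccine (AERAS-404 and BCG) with power of 80" percent. Schoenfeld events per vaccine-placebo pair: 4 × (1.2816 + 0.8416)² / (ln 0.5)² = 37.5, so 38. If one vaccine works and the other does not, the total is 38 × 2.5/1.5 = 63.3, so 64. This agrees with "a total sample size of 990 is expected to provide 64 primary QFT-GIT conversion endpoints".

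**True cumulative conversion, counted from Day 84.** 1 − exp(−0.10 × days/365.25):
- Month 6 (84 days): 2.3%
- Month 12 (252 days): 6.7%
- Month 18 (420 days): 10.9%
- Month 24 (588 days): 14.9%

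**Closed form for the end of the curve.** Conversion probability at the last visit: p = 1 − exp(−0.10 × 168/365.25) = 4.5%. Survival after Month 18: 0.8914. With dates uniform over 29 days, the last-window hazard is p × (1 + 1/2 + … + 1/29) = 0.04495 × 3.96 = 0.178. The curve ends at 1 − 0.8914 × exp(−0.178) = 25.4%. If all of the roughly 263 attenders have distinct times, the harmonic sum is 6.15 and the curve ends at 1 − 0.8914 × exp(−0.276) = 32%.

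**Simulation.** One arm of 330, 2,000 replicates, conversions detected at the visits, product-limit estimate on exact dates:

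| Spread of dates, clock | Mean end of curve |
|---|---|
| Uniform, Day 0 | 26.0% |
| Clustered, Day 0 | 28.1% |
| Uniform, Day 84 | 29.9% |
| Clustered, Day 84 | 31.3% |

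The median is about 25-26%. On the Day 84 clock the 5th-95th percentile is about 16-64%. A curve reaches 100% in about 0% of runs (uniform, Day 0 clock) to 4% (Day 84 clock). Just before the Month 24 window the curve stands at 11.0%, against a true 10.9%. With the same data placed on scheduled visits, it ends at 14.8-14.9%.

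**Other conversion rates.** At 5% per year: true 7.7%, mean end of curve 14-16%. At 17% per year: true 23.9%, mean 40-45%.

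**Reading the per-visit table.** At nominal visit days only the tests done so far in each window count: Month 6 gives 1.1-1.2% (true 2.3%), Month 12 about 4.5% (6.7%), Month 18 about 8.9% (10.9%) and Month 24 13.7-13.9% (14.9%). At 24 four-week months on the Day 84 clock, 672 days after that visit, all in-window Month 24 tests are past and the row carries the full inflation.

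**Effect on inference.** With a true hazard ratio of 0.5, the Cox estimate averages 0.491 on exact dates and 0.490 on scheduled visits.

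**The case against.** The strongest reply is that this is a display artefact. No decision rule uses the end of the curve, vaccine efficacy is one minus the Cox hazard ratio, and the test and hazard ratio barely move. That stands. A reader might infer that the primary comparison is biased; it is not, provided attendance timing is similar across arms.

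Second, the Kaplan-Meier outputs are not the SAP's only absolute estimates. SAP 14.1.2 tabulates the number and percentage converting per arm. Its table of first conversion by visit requires a result at that visit for a participant to count as at risk, so its denominators are already correct. This stands too. It also means the report would show about 4.5% converting at Month 24 in one table, beside a curve that typically rises some 15 points over the same visit.

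Third, the per-visit Kaplan-Meier table might be read at the nominal day, where Month 24 comes out near 13.8%. A reader might infer that the table will print a doubled Month 24 rate. The documents do not establish that, because no read-off time is given. But the nominal reading that spares Month 24 understates Months 6, 12 and 18.

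Fourth, a visit-rounded life-table figure and an interval-censored model are planned. The model supports the hazard-ratio table, not these curves. The life table counts each participant censored in an interval as half at risk. With Month 24 events and negatives in the same interval, the last step becomes 0.045/(0.5 + 0.0225) = 8.6% instead of 4.5%, and the curve ends at 1 − 0.8914 × 0.914 = 18.5%.

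**Conclusion.** The concern holds for the Kaplan-Meier figures and the per-visit rates, as a reporting error. The typical primary-endpoint curve ends at about 1.7 times the true value (about 25-26% against 14.9%). The mean is 26-31% because the distribution is skewed, and single curves vary widely. The distortion of the tail is confined to the last window. The direction follows from the stated rules; the size rests on the protocol's 10% per year rate, 7% per year loss and the assumed spread of test dates.

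Two stronger readings should be resisted. A jump to 100% is possible but uncommon for visits within window. The primary-endpoint figures also do not carry over to sustained conversion. Those curves share the mechanism, but SAP 14.2.3 censors non-sustained converters at their last result, which can fall after the Month 24 window. Under an assumed 20% reverting, the end of that curve was about 20.5% against a true 11.9% (0.8 × 14.9%), and no curve reached 100%.

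**What to change.** In SAP 14.1.3 and 14.2.3, for all Kaplan-Meier tables and figures of conversion and sustained conversion, set both event and censoring times to the scheduled visit of the test: Month 6, 12, 18 or 24, which is 3, 9, 15 or 21 months on the Day 84 clock. Where SAP 14.2.3 censors at a post-conversion test, use that visit's scheduled month. State in SAP 14.1.2 which clock applies and that the event rate is reported at the scheduled visit. A Turnbull (interval-censored) estimate is an acceptable alternative and also deals with missed visits.

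Censoring Month 24 negatives at the end of the window is not equivalent: it repairs the tail but leaves the low readings at the nominal days of the earlier visits.

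The cost is one derivation rule and a rerun of existing outputs. No new data are needed, and the log-rank test, hazard ratio and vaccine efficacy stay essentially the same.

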**Study Day 84 (Subjects receiving BCG)**

*Allowable window for clinic visit is 84±7 days from Day 0*

1. Interval medical history and, if indicated by history, focused physical examination.
2. Monitor participant for serious adverse events, adverse events of special interest, and SUSARs; record concomitant medications
3. Monitor participant for solicited and unsolicited injection site reaction adverse events; record concomitant medications
4. Complete Study Day 0 study injection site examination (with photograph if there is a visible injection-site abnormality; see Section 5.7 for further details)
5. TB Symptom Screen
6. Blood collection
  - QuantiFERON®-TB Gold In-Tube
  - Whole blood for novel IGRA

**Study Month 6, 12, 18 and 24 (Study Days 168, 336, 504, and 672) (Subjects receiving BCG; to be completed by subjects who did not convert from QFT-GIT(-) to QFT-GIT(+) at the previous visit)**

*Allowable window for clinic visit is 6, 12, 18, or 24 months (168, 336, 504, 672 days) ±14 days from Day 0*

1. Interval medical history and, if indicated by history, focused physical examination.
2. Monitor participant for serious adverse events, adverse events of special interest, and SUSARs; record concomitant medications
3. TB Symptom Screen
4. Blood collection
  - QuantiFERON®-TB Gold In-Tube
  - Whole blood for novel IGRA
  - [Study Months 6 and 12 only]PBMC and plasma for correlates of risk protection
  - Whole blood for RNA extraction/absolute blood count

**Study Month 6 (Study Day 168) (Subjects receiving BCG; to be completed by subjects who converted from QFT-GIT(-) to QFT-GIT(+) at Study Day 84)**

*Allowable window for clinic visit is 6 months (168 days) ±14 days from Day 0*

1. Monitor participant for serious adverse events, adverse events of special interest, and SUSARs; record concomitant medications
2. TB symptom screen

**84 and 168 Days after conversion from QFT-GIT(-) to QFT-GIT(+) at Months 6-24 (Subjects receiving BCG; to be completed by subjects who converted from QFT-GIT(-) to QFT-GIT(+) at Month 6-24 visits)**

*Allowable window for clinic visit is 84 or 168 days ±14 days after conversion*

1. Monitor participant for serious adverse events, adverse events of special interest, and SUSARs; record concomitant medications
2. TB symptom screen
3. Blood collection
  - QuantiFERON®-TB Gold In-Tube

- Whole blood collection for RNA extraction/absolute blood count

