**Study Day 56 (Subjects receiving AERAS-404 or placebo)**

*Allowable window for clinic visit is 56-2/56+14 days from day 0*

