  - Vaccine efficacy is derived as:
    - o  $VE = 1 - Hazard\ Ratio\ (Vaccine/comparator)$
    - o The hazard ratio is estimated based on the following Cox regression model:

```
PROC PHREG DATA = <>;
    MODEL Time to Event (Months) * Censor (1) = Treatment_Group;
RUN;
```

- Censor = 1 represents censored participant.
      - Censor = 0 represents participant who experienced an event.
      - Months represent the available follow-up time (months) per participant since Day 84.
    - o The 80% CI is based on the two-sided hazard ratio confidence interval and will be derived as:
      - $VE_{lower\ limit} = 1 - Hazard\ ratio_{upper\ limit}$
      - $VE_{upper\ limit} = 1 - Hazard\ ratio_{lower\ limit}$
    - o The 95% CI is based on the two-sided hazard ratio confidence interval.

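### The final-analysis log-rank test appears to start its clock at Day 84, which may fall later in placebo than in BCG, while the primary Cox model starts at randomization

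*SAP*

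**What the plan says.** SAP 14.1.3 gives one LIFETEST call, with a test on treatment group, for every Kaplan-Meier analysis. Its time variable is months from "Day 84 (applicable to analyses based on the mITT and PP analysis set"; analyses of the randomized set count from randomization instead. The primary-endpoint Kaplan-Meier figure in 14.1.2 is also measured from Day 84.

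The same section gives the primary Cox model, the source of the hazard ratio, vaccine efficacy (VE) and 80% confidence interval, a different origin: "Months represent the available follow-up time (months) per participant since randomization". For sustained conversion, the Cox model in 14.2.3 goes back to Day 84: "Months represent the available follow-up time (months) per participant since Day 84". SAP 14.1.2 puts the one-sided log-rank p-value and the Cox results in one table.

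Protocol Appendix A schedules the Day 84 visit differently by arm:
- BCG: "Allowable window for clinic visit is 84±7 days from Day 0".
- AERAS-404 or placebo: "Allowable window for clinic visit is 28±5 days from Day 56". The Day 56 visit has its own rule: "Allowable window for clinic visit is 56-2/56+14 days from day 0".
- Months 6, 12, 18 and 24 are days 168, 336, 504 and 672, each ±14 days, counted from Day 0 in every arm.

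SAP Appendix 8 lists a single Day 84 window, 84 ± 7 days from Day 0, with no split by arm. Under 14.1.3, a participant without the endpoint is censored on the date of the last non-positive test. Protocol 7.3 states that the two vaccine-versus-placebo log-rank tests "will be performed with a 1-sided Type 1 error of 0.1".

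**The concern.** Two problems follow. First, the p-value and the confidence interval for one comparison, printed in one table, would rest on different time axes. They could disagree near the decision boundary for a reason that has nothing to do with the vaccine.

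Second, if the clock starts at the actual Day 84 visit, its start depends on the arm. A late second dose delays that visit in placebo but has no counterpart in BCG, and all later tests stay fixed to Day 0. Deferral therefore shortens measured follow-up in placebo only. BCG versus placebo is one of the two primary comparisons and carries no multiplicity adjustment, and the distortion favors BCG revaccination.

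**Working it through.** **1. The plan's own figures.** Protocol 7.6 assumes a 50% reduction, "power of 80% and a type 1 error rate of 10% (1-sided"), 64 endpoints, 10% conversion and 7% loss per year. For one vaccine-placebo pair, events needed = 4(z0.90 + z0.80)² / (ln HR)² = 4(1.2816 + 0.8416)² / (0.6931)² = 18.03 / 0.4805 = 37.5, so 38. If one vaccine works and the other does not, the working pair holds 1.5/2.5 = 60% of events: 64 × 0.6 = 38.4, which gives power 80.7%. Simulated endpoints at 21 months are 25.3 + 25.3 + 13.1 = 63.7, against 64 stated. The design figures reproduce, so 10% is the right benchmark.

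**2. Where Day 84 can fall (study days).**
- BCG: 84 − 7 = 77 to 84 + 7 = 91.
- AERAS-404 or placebo: 54 + 28 − 5 = 77 to 70 + 28 + 5 = 103.

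The dose may be 2 days early but 14 days late, so the possible shift is almost all toward a later placebo visit. Days 92 to 103 meet the protocol but fall outside SAP Appendix 8.

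**3. Mechanism.** On an actual-visit clock, a Month 24 test on day 672 comes 672 − 84 = 588 days (21.0 four-week months) after a Day 84 visit made on time, but only 574 days (20.5 months) after one delayed by 14 days. Non-converters are censored at that test, so placebo participants leave the final risk set before BCG participants. The log-rank expected count for BCG sums n_BCG/n over event times. Late placebo events meet a nearly full BCG set, and BCG events meet a depleted placebo set. Both raise the expected BCG count above what equal hazards justify and push z toward BCG. At Months 6 to 18 most non-converters stay at risk, so the effect there is small.

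**4. Size under no vaccine effect.** Assumptions: 330 per arm; 10% per year conversion after a negative Day 84 test; 7% per year loss; visits uniform within protocol windows; event and censoring times equal to test dates, with no rounding before ranking; rejection at z < −1.2816; final analysis; 10,000 replicates (Monte Carlo error about 0.3 to 0.5 points). The deferral share is assumed. Deferred doses are spread evenly over 1 to 14 days (mean 7.5), so the mean delay is share × 7.5.

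| Share deferred | Mean delay (days) | Error, actual-visit clock | Error, nominal day-84 clock |
|---|---|---|---|
| 0% | 0 | 10.9% | 10.4% |
| 10% | 0.75 | 11.9% | 10.1% |
| 20% | 1.5 | 13.4% | 9.6% |
| 30% | 2.3 | 16.3% | 9.7% |
| 50% | 3.75 | 19.4% | 9.7% |
| 100% | 7.5 | 31.6% | 8.7% |

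The nominal-day clock subtracts a constant from every time, so it ranks participants exactly as a randomization clock does. A separate simulation gave 11.7%, 11.8%, 13.8% and 17.9% at mean delays of 0, 0.75, 1.5 and 3 days, against 9.4% to 10.8% on the randomization clock. At the extremes, doses uniform over days 54 to 70 give 25.6%, and every dose on day 70 gives 52.4%. If actual Day 84 visits keep to 84 ± 7 days in all arms, the error is 9.6%.

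**5. What is untouched.** AERAS-404 and placebo share one schedule, so their comparison is unaffected. The primary Cox model counts from randomization. The interval-censored sensitivity model in 14.1.3 uses nominal visit months.

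**The case against.** The strongest reply is that the SAP never says Day 84 is the visit date. On the nominal-day reading, or if visits kept to Appendix 8, there is no inflation. That stands as a limit on the claim. The text still leans toward the visit: 14.1.3 derives follow-up for each participant from a date, Day 84 is listed among the visits, and mITT membership depends on the result at that visit. Appendix 8 is used in 14.1.3 to classify test timing, and a compliance label does not move the dates on which visits took place.

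The clock behind the p-value is also partly inferred. The Day 84 origin is attached to the Kaplan-Meier code, 14.1.3 lets the origin depend on the table, and the table shells are not available. A Cox score test is itself a log-rank statistic, so a programmer could take the p-value from the model on the randomization clock. Hence the claim is only that the test appears to use Day 84.

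The deferral pattern is unknown, and Protocol 3.5 describes deferral for short-term reversible conditions, not as routine. A reader might infer that the true error is 13-17%. The documents do not support that as a fact, because it needs both the visit-date reading and an assumed mean delay of a few days. The direction is firmer than the size, since the dose window allows far more lateness than earliness.

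Coarse rounding of months would create ties and reduce the effect. The planned interval-censored analyses are a genuine safeguard, but as sensitivity analyses they do not replace the stated test.

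**Conclusion.** The conflict of clocks within SAP 14.1.3, and between 14.1.3 and 14.2.3, is documented and needs no assumption. The bias toward BCG is conditional on Day 84 being the actual visit date and on the log-rank test using that clock. Under those readings the one-sided error for BCG versus placebo is about 11-12% with little or no deferral, about 13-18% at a mean deferral of 1.5-3 days, and higher if deferral is common. Otherwise it is about 9-10%.

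Three wider inferences are tempting but not supported:
- **Primary VE and its 80% interval are biased.** They come from the Cox model on the randomization clock.
- **The endpoint-triggered primary analysis is affected.** SAP 4.2 says it was completed under a separate SAP; this document governs the final analysis.
- **The secondary hazard ratio is biased by a known amount.** For BCG versus placebo it is exposed to the same mechanism, but sustained conversion has fewer events and different censoring, and the size has not been quantified.

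The H4:IC31-versus-BCG comparison added for the sponsor's partner compares the same two schedules and is exposed too, but it is not a primary comparison.

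**What to change.** Specify one clock, time since randomization (Day 0) with entry at Day 84, for the log-rank, Kaplan-Meier and Cox analyses of the primary, per-protocol, secondary and end-of-study sustained endpoints. This means replacing the Day 84 origin with randomization in SAP 14.1.3 and 14.2.3 and in the matching figure descriptions in 14.1.2, 14.2.2 and 14.3.2, and naming the clock for the end-of-study sustained Cox model.

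Delayed entry costs nothing here: the latest in-window Day 84 visit is day 103 and the earliest in-window Month 6 test is day 168 − 14 = 154, so every in-window participant has entered before the first event. Some mild conservatism can remain if deferral is heavy (8.7% at a mean delay of 7.5 days).

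Separately, the Day 84 window for AERAS-404 and placebo in Protocol Appendix A and the single window in SAP Appendix 8 must be reconciled.

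The cost is SAP wording and one derived time variable. Endpoints, test dates and data collection do not change. The change should be made before unblinding for the final analysis.
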